3.3.3. End-points

Primary End-point:

1. Progression Free Survival (PFS) for patients with ad/mRCC receiving SU.

PFS is defined as: the time from when the patient receives the first dose of SU to the time of progression or death due to any cause, which occurs first.

2. Time to Treatment Failure (TTF) for SU 1st line.

TTF is defined as: from when the patient receives the first dose of SU to the time of SU discontinuation (date completed by the physician).

Secondary End-point:

1. Objective Response Rate (OOR) for adv/mRCC patients receiving SU as 1st line treatment.

ORR is defined as the percentage of patients with confirmed CR or confirmed PR according to RECIST criteria v1.1.

2. Description of SU real life usage of doses across all centers, including description of treatment schedules (dose change, dose schedule, average dose received during the period treatment).

3. Combined PFS for patients with ad/mRCC receiving the 2nd line sequence SU- different treatment.

Combined PFS is defined as: the time from when the patients receives the first dose of SU as first line, until progression or death due to any cause while on the 2nd line treatment, whichever occurs first during the 2nd line sequence treatment.

4. Combined TTF for the SU-2nd line sequence.

Combined TTF is defined: as the time from when the patient receives the first dose with SU as first line, to the time of 2nd line sequence discontinuation (date completed by the physician).

5. OS for adv/mRCC patients receiving SU as first line followed by 2nd line as measured from date of first SU dose to the date of death of any cause. The OS median and the overall survival at month 24 (24 months OS) will be measured.
6. If possible, efficacy parameters (PFS, OS) for the combined 1st line SU- 2nd line sequences according to the second line post SU (other than SU-AXI):
 - SU in 1st line-Axitinib TKI in 2nd line.
 - SU in 1st line- other TKI in 2nd line (sorafenib, pazopanib).
 - SU in 1st line/mTOR in 2nd line (temsirolimus, everolimus).
7. Safety description with AE listing in patients receiving SU: frequencies of patients experiencing at least one AE will be displayed by body system.
8. QoL using the questionnaire Functional Assessment of Cancer Therapy-Kidney Symptom Index 19 (FKSI-19).

CCI

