3.4. Study Design and Study Population

OPTIMISE is an international (AfME), prospective, non-interventional, non-controlled, observational multicenter study.

Patients would be enrolled from several AfME countries including Algeria, Morocco, Tunisia, Egypt, UAE, Qatar & South Africa.

Investigators will be specialists in charge of adv/mRCC. These sites involved (at least when performing feasibility) will be representative of their respective countries in terms of practice. Participating physicians will not be influenced in their decision making and routine proceedings in any way.

Primary outcome measure will assess progression free survival (PFS) in patients receiving the SU and in patients receiving a second line treatment post SU; as well as TTF for patients with adv/mRCC.

Patients will be enrolled when they start a treatment with SU on 1st line. Patients enrolled at SU initiation, will be followed-up whatever the post 2nd line SU- different sequence treatment is (AXI, other drugs, no further active treatment, (supportive care)). The possible 1st and 2nd line sequences of treatment under investigation (ie, patient pools) will be ([Figure 1](#)):

- SU-AXI.
- SU- other second line treatment (sorafenib, pazopanib, everolimus, temsirolimus, other).
- SU- not further active treatment (supportive care).

The study will include a prospective data collection:

- Prospective data will be collected for all patients enrolled in the study at SU-1st line level, irrespective of 2nd line sequence treatment, or no further active treatment.
- Prospective data in terms of medical treatment records will be collected for all 2nd line patients.

The inclusion period of eligible patients is planned for 12 months, with minimum of 1 year follow-up period. Patients will be followed-up from their enrollment to the end of the study follow-up period.

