8.1. Efficacy analyses

8.1.1. Survival analyses

▪ Role:

- To meet primary and secondary objectives
- To assess the impact of SU as a first line therapy on progression free survival (PFS) and on time to treatment failure (TTF) for patients with adv/mRCC in real life setting;
- To assess the impact of the SU–other sequence on combined PFS and TTF for patients with adv/mRCC.
- To assess the Overall Survival (OS) (OS median and 24-month OS) for adv/mRCC patients receiving SU in first line followed by other sequence in 2nd line;
- To assess the time to strategy failure (TSF) for adv/mRCC patients receiving the SU–other sequence;
- To assess PFS and OS for the combined 1st line SU – 2nd line sequences according to the second line post SU (TKI, mTOR) treatment; (specific objective – “SU – TKI/mTOR” patients)

▪ Population:

- “SU – other sequence” patients
- “SU – TKI / mTOR” patients

▪ Endpoints:

- Progression Free Survival (PFS)
- Combined PFS
- Time to Treatment Failure (TTF)
- Combined TTF
- Time to Strategy Failure (TSF)

- Overall Survival (median OS and 24-month OS rate)
- **Subgroups:**
- Type of 2nd line treatment post SU: “SU – TKI / mTOR” patients (**SUT-TKI and SUT-mTOR**)
(only combined PFS and OS endpoints)
- **Statistical methods:** Survival analysis methods.
- **Method for handling missing values:** see guideline in chapter 7.

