9.2. Initial dose and schedule of SU in the first line treatment

Initial dose SU	N(%)
50mg	
37.5mg	
25mg	
Other	
Schedule	N(%)
4 weeks on, two weeks off	
Continous	

[figure not shown]
Other	
-------	--

9.3. Cross tabulation of efficacy end points(PFS,OS,ORR,TTF) for both first line SU treatment as well as for the SU- second line therapy

Efficacy endpoints (months±SD)	Overall	First line SU	Second line therapy				
			SU-Bsc	SU-AXI	SU/TOR	SU/TKI	
PFS							
OS							
ORR							
TTF							

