Appendix 3: List of covariate and outcomes in the study

Variable	Role	Operational definition
Age	Covariate	Defined as the date of birth of the participant
Gender	Covariate	Defined as the male or female sex
Ethnicity	Covariate	Defined as race of Middle Eastern, Indian, Caucasian or African descendant
ECOG	Covariate	The ECOG Scale of Performance Status describes a patient's level of functioning in terms of their ability to care for themselves, daily activity, and physical ability (walking, working, etc.)
Number of metastatic sites	Covariate	Total number of site where metastasis is detected
Nephrectomy	Covariate	Surgical removal of the kidney
MSKCC risk	Covariate	The MSKCC risk system stratifies patients with mRCC into poor-, intermediate- and favorable-risk categories based on the number of adverse clinical and laboratory parameters present
Hypertension	Covariate	Presence of high systolic blood pressure >13mmHg
Previous medical treatment	Covariate	Presence of medical treatment related to the disease prior to SU initiation
PFS	Outcome	The PFS will be defined as the time from when the patient receives the first dose of SU to the time of progression or death due to any cause, whichever occurs first
OS	Outcome	OS defined as the time from date of first SU dose to the date of death of any cause.
ORR	Outcome	The objective response rate is the percentage of patients with a complete response (CR) or a partial response (PR) according to RECIST 1.1 criteria as best response, over the SU treatment period.
TTF	Outcome	TTF is defined as the time from when the patient receives the first dose of treatment to the date of SU discontinuation
Combined PFS	Outcome	The time from when the patients receives the first dose of SU as first line, until progression or death due to any cause while on the 2nd line treatment, whichever occurs first during the 2nd line sequence treatment.
Combined TTF	Outcome	The time from when the patient receives the first dose with SU as first line, to the time of 2nd line sequence discontinuation

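### Median and 24-month OS are tied to patients who reach second line but timed from the first SU dose, and the SAP elsewhere implies OS in everyone: one all-treated OS population is needed

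*Protocol*

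**What the plan says.** Protocol 3.3.3, secondary end-point 5, defines "OS for adv/mRCC patients receiving SU as first line followed by 2nd line as measured from date of first SU dose" to death from any cause. It continues: "The OS median and the overall survival at month 24 (24 months OS) will be measured". SAP 8.1.1 gives the role of the OS analysis, again naming the median and the 24-month rate, as "for adv/mRCC patients receiving SU in first line followed by other sequence in 2nd line". The populations listed there are the SU–other sequence and SU–TKI/mTOR patients. SAP 7.4 plans Kaplan-Meier curves, with no delayed entry, landmark or second-line time origin.

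Two other places in the SAP read differently. Appendix 3 has "OS defined as the time from date of first SU dose to the date of death of any cause", with no condition on second line. Table shell 9.3 is titled "Cross tabulation of efficacy end points(PFS,OS,ORR,TTF) for both first line SU treatment as well as for the SU- second line therapy". Its OS row has columns for Overall, First line SU, SU-Bsc, SU-AXI, SU/TOR and SU/TKI.

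On follow-up, Protocol 3.4 states: "Prospective data will be collected for all patients enrolled in the study at SU-1st line level, irrespective of 2nd line sequence treatment". Protocol 3.5 and 8.2 add six-monthly survival follow-up after SU. Protocol 3.4 also lists SU followed by supportive care among the possible first- and second-line sequences.

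**The concern.** Whether a patient belongs to the OS set is known only once second line starts, yet time is counted from the first SU dose. A patient who dies on SU cannot enter the set. A patient who does enter could not have died between the first SU dose and second-line start, but Kaplan-Meier counts that interval as time at risk. This is immortal time. It affects the single-cohort median and 24-month rate themselves, before any second-line drugs are compared.

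Protocol 3.3.1 names two aims: outcomes of SU use, and outcomes of the SU–second-line sequence. The restricted OS serves neither well. It is not survival of patients starting SU, and as survival of second-line recipients it lacks delayed entry. Because other SAP text implies OS in everyone, an analyst could report either of two quite different numbers and cite the plan for both.

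**Working it through.** **1. The plan's own figure.** No OS figure is stated. The only sample-size figure is for ORR (Protocol 8.7): 1.96 × √(0.37 × 0.63 / 140) = 0.080, which reproduces the ±8%. It has no bearing on OS.

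**2. Who is in the OS set.**

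| Patient | End-point 5 and SAP 8.1.1 | Appendix 3 and shell 9.3 |
|---|---|---|
| Dies on SU | out | in |
| Still on SU at cut-off | out | in |
| SU, then supportive care | unclear | in |
| SU, then active second line | in | in |

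**3. Possible size (illustration).** Inputs:

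- Median time on first-line SU: 5.9 or 10.5 months, the community and academic figures cited in Protocol 6.1.1. Used as exit from SU for any reason, death included, at rate r = ln 2 / median.
- Horizon T = 24 months, from end-point 5.
- Death hazards λ1 on SU and λ2 after SU: assumed.
- Second line starts at SU exit in those alive, or in a share of them unrelated to prognosis: assumed.

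Formulas:

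- All SU patients: S(T) = e^(−rT) + (r − λ1)(e^(−λ2·T) − e^(−rT)) / (r − λ2). With λ1 = λ2 = λ this is e^(−λT).
- Patients in second line by T, timed from first SU dose: r(e^(−λ2·T) − e^(−rT)) / [(r − λ2)(1 − e^(−rT))].

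Example with SU median 5.9 and true OS median 24: r = 0.1175, λ = 0.0289, e^(−λT) = 0.500, e^(−rT) = 0.0596. Restricted value = 0.1175 × 0.4404 / (0.0886 × 0.9404) = 0.621, against 0.500 in all patients.

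Constant death hazard, 24-month OS:

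| True median OS (months) | All SU patients | Second line only, SU 5.9 | Second line only, SU 10.5 |
|---|---|---|---|
| 12 | 25.0% | 39.8% | 45.2% |
| 18 | 39.7% | 53.3% | 57.9% |
| 24 | 50.0% | 62.1% | 66.0% |
| 30 | 57.4% | 68.1% | 71.5% |

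The excess is 10.7 to 14.8 points (SU 5.9) or 14.0 to 20.2 points (SU 10.5). The top value is an extreme case: with SU median 10.5 and OS median 12, the model has λ/r = 87.5% of patients dying on SU. In the other cells that share is 20% to 58%.

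**4. Higher mortality after SU.** Take a death-hazard median of 48 months on SU:

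| Median after SU (months) | SU time (months) | All SU patients | Second line by month 24 |
|---|---|---|---|
| 12 | 5.9 | 38.8% | 39.8% |
| 12 | 10.5 | 48.6% | 45.2% |
| 6 | 10.5 | 35.4% | 23.9% |

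The sign changes because patients still on SU at month 24, all alive, are also left out: e^(−rT) is 6% of the cohort for SU 5.9 and 21% for SU 10.5.

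**The case against.** The strongest reply is that the plan does not confine OS to second-line patients throughout. Appendix 3 is unrestricted, and shell 9.3 has Overall and First line SU columns. Part of the SAP between the subgroup section and the safety endpoints is redacted or missing, so fuller OS text may exist. The SAP 8.1.1 population labels also cover first-line PFS and TTF, so they cannot safely be read as switchers only. This stands. A reader might infer that the plan has no OS outside switchers; the documents support only that the places conflict. The explicit wording of end-point 5 and of the SAP 8.1.1 role remains, and it is the only visible text that ties the 24-month rate to a population.

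A reader might also infer that everyone without active second-line treatment is excluded. That is not established, because supportive care is a listed sequence and SU-Bsc sits under second-line therapy in shell 9.3. Only deaths on SU and patients still on SU clearly fall outside.

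Nor do the documents support the inference that sites where fewer patients reach second line would look better. In the model above, a switching share unrelated to prognosis cancels from the restricted estimate.

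Finally, OS is one of several secondary end-points, Protocol 8.11 calls the study hypothesis-generating, and the primary end-points, PFS and TTF, are not defined with a second-line condition. This limits the severity but does not repair the definition.

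**Conclusion.** The OS definition is wrong as written and should be fixed, at the weight of a secondary end-point. End-point 5 and the SAP 8.1.1 role select on reaching second line while timing from the first SU dose, so they do not estimate survival from SU start. Other SAP text points to a different population, and the status of supportive-care patients is open.

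It is tempting to say flatly that survival will be overstated by a given amount. The documents give no OS rate, no share reaching second line and no number of deaths on SU. Overstatement is the expected direction. The 11 to 20 points at month 24 rest on exponential times, equal death hazards on and after SU, and switching unrelated to prognosis. With much higher mortality after SU and follow-up cut at month 24, the gap shrinks and can reverse. In either direction the number is not OS from SU start, so the remedy is the same.

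**What to change.** - In Protocol 3.3.3 end-point 5 and SAP 8.1.1, define median and 24-month OS from first SU dose in all enrolled patients who received at least one dose, whatever follows: second line, supportive care, continued SU, or death on SU.
- State that the efficacy population in SAP 4.1, which requires at least 6 months of follow-up, does not apply to OS. That condition would itself remove early deaths.
- If OS in second-line recipients is also wanted, report it separately. Either keep the first-dose origin with delayed entry at second-line start, or time it from second-line start. Label it as conditional on reaching second line.
- Align shell 9.3 and Appendix 3 with this, and state whether supportive-care patients count as a second-line sequence.

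The cost is wording. Survival is already to be followed in every enrolled patient, so no new data, visits or patients are needed. The reported OS will probably be lower.

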3.4. Study Design and Study Population

OPTIMISE is an international (AfME), prospective, non-interventional, non-controlled, observational multicenter study.

Patients would be enrolled from several AfME countries including Algeria, Morocco, Tunisia, Egypt, UAE, Qatar & South Africa.

Investigators will be specialists in charge of adv/mRCC. These sites involved (at least when performing feasibility) will be representative of their respective countries in terms of practice. Participating physicians will not be influenced in their decision making and routine proceedings in any way.

Primary outcome measure will assess progression free survival (PFS) in patients receiving the SU and in patients receiving a second line treatment post SU; as well as TTF for patients with adv/mRCC.

Patients will be enrolled when they start a treatment with SU on 1st line. Patients enrolled at SU initiation, will be followed-up whatever the post 2nd line SU- different sequence treatment is (AXI, other drugs, no further active treatment, (supportive care)). The possible 1st and 2nd line sequences of treatment under investigation (ie, patient pools) will be ([Figure 1](#)):

- SU-AXI.
- SU- other second line treatment (sorafenib, pazopanib, everolimus, temsirolimus, other).
- SU- not further active treatment (supportive care).

The study will include a prospective data collection:

- Prospective data will be collected for all patients enrolled in the study at SU-1st line level, irrespective of 2nd line sequence treatment, or no further active treatment.
- Prospective data in terms of medical treatment records will be collected for all 2nd line patients.

The inclusion period of eligible patients is planned for 12 months, with minimum of 1 year follow-up period. Patients will be followed-up from their enrollment to the end of the study follow-up period.

3.5. Setting

The study will enroll patients according to the eligibility criteria in participating countries across Africa Middle East. The recruiting centers will be representative of each country involved in terms of care management systems, of size and of practices (at least when performing feasibility).

Any patient who meets the eligibility criteria will be invited to participate in the study with no selection by the investigators. The enrollment visit will be performed at the time of the patients' inclusion, after the patients' acceptance of enrollment in the study.

Data will come from medical records and will be collected in routine clinical practice. The enrollment visit will comprise a first section on patients' eligibility for every patient.

Follow-up will be ensured during visits in the context of usual patients' care management (non-interventional study). As long as the patients are treated with SU, AXI, other TKI (sorafenib, pazopanib everolimus, temsirolimus, other) or no further active treatment (supportive care), every visit to the center will be recorded. In accordance with ESMO guidelines and physicians clinical practice is real life, follow-up visits are approximately expected as below:

- During SU treatment: every 6 weeks (every cycle) with tumor assessment approximately every 3 months with respect to the clinical practice.
- When patients come off SU treatment: they will be followed-up every 6 months for survival until the end of the study.
- A deviation of +/- 6 weeks (1.5 months) is acceptable window for the follow-up visits.

Because of the inclusion criteria (patients being treated with SU in 1st line according to the approved therapeutic indication), the medication prescribed within the regular practice of the physician. Because of the non-interventional nature of the study, there will be no specific requirements in regards to the treatment process. The physician will determine dosage and duration of the treatment as guided by the local approved country. Prescribing information will be according to his assessment of the individual therapeutic needs of the patient.

4. AMENDMENTS AND UPDATES

Any change in the study plan requires a protocol amendment. An investigator must not make any changes to the study without IRB/IEC and sponsor approval except when necessary to eliminate apparent immediate hazards to the subjects. A protocol change intended to eliminate an apparent immediate hazard to subjects may be implemented immediately, but the change must then be documented in an amendment, reported to the IRB/IEC within 5 working days, and submitted to the appropriate regulatory agency in the required time frame. All protocol amendments must be reviewed and approved following the same process as the original protocol.

5. MILESTONES

Milestone	Planned date
Completion of feasibility assessment	Aug-2016
Start of data collection FSFV	Sep-2016
End of data collection, last subject last visit (LSLV)	Sep-2019
Final study report	Jan-2020

6. RATIONALE AND BACKGROUND

According to the WHO GLOBOCAN program, the annual incidence of RCC (renal cell carcinoma) is 213,924 people, with 90,802 deaths per year leaving a 5-year prevalence of 580,700 people. RCC is age-related (ie, more common in older patients) and is most common in the more developed countries of the world like the United States and countries of Europe. In the United States, the ASR (age-specific rate) of RCC is 12.0 per 100,000 people. Most Arab countries of the Middle East have rates between 2.0 and 3.0. Turkey has the highest ASR of 5.6 for RCC.¹

Most of the figures are likely inaccurate and underestimate the true incidence of RCC as data is not consistently shared among countries and institutions within countries. Recently Ghosn et al, reported results from The Africa–Middle East Genitourinary Tumor Working Group questionnaire distributed between 2011 and 2012 to a network of reference oncologists across North Africa and the Middle East, identified through institutions, professional organizations, and personal contacts. Similar to other countries around the world, most RCC are low-grade, early stage tumors, however the significant proportion of patients that present with high-stage or metastatic disease mirrors the 20-30% seen globally.²

In the 1990's, the mainstays of mRCC treatment consisted of systemic cytokine therapies such as high-dose systemic interleukin-2 (IL-2) or interferon-alpha (IFN- α). Molecular research into the pathogenesis of RCC has provided valuable information on the signaling pathways known to be altered in RCC, including vascular endothelial growth factor (VEGF), its receptor (VEGFR) and the mammalian target of rapamycin (mTOR), a key kinase regulating cell growth and proliferation, cellular metabolism, and angiogenesis.

Molecularly targeted therapies were developed specifically to target the signal transduction pathways. Recently, several targeted therapies have become available for first- and second-line treatment of mRCC.³

New treatment options include the multitargeted receptor tyrosine kinase inhibitors (TKIs) Sunitinib (Sutent \circledR , Pfizer Inc.), sorafenib (Nexavar \circledR , Bayer HealthCare/Onyx pharmaceuticals), pazopanib (Votrient \circledR , GlaxoSmithKline Inc), Cabozantinib (Cometriq \circledR , Exelixis) and axitinib (Inlyta \circledR , Pfizer Inc); the VEGF ligand binding monoclonal antibody bevacizumab (Avastin \circledR , Genentech, Inc.), usually given in combination with IFN- α ; and the mTOR kinase inhibitors temsirolimus (Torisel \circledR , Pfizer Inc) and everolimus (Afinitor \circledR , Novartis), in addition to Nivolumab (Opdivo \circledR , Bristol-Myers Squibb). These new agents have dramatically changed the management of mRCC in the last 5 years and the current international guidelines recommend a number of these new treatment options for first- and second-line treatment based on category 1 to 3 evidence.⁴

